2.3. Final Analysis

The study will be unblinded and final analyses will be performed when all subjects have completed the study, unresolved challenges have been resolved or confirmed to be unresolvable, and data have been cleaned and locked.

3. GENERAL CONSIDERATIONS FOR DATA ANALYSIS

3.1. Data Handling

Descriptive statistics will be used to analyze the results. For categorical variables, the number and percentage of subjects in each category will be listed; for continuous variables, the number of subjects (n), mean, standard deviation (SD) or standard error (SE), median, first quartile (Q1), third quartile (Q3), minimum and maximum values will be listed.

Unless otherwise stated, all statistical tests are two-sided with a significance level of 5%.

The number of decimal places in which consecutive data are summarized:

- For minimum (min) and maximum (max) values, the number of decimal places displayed is the same as the data collected.
- Mean, median, geometric mean, first quartile (Q1), and third quartile (Q3), show one more decimal than the collected data. Standard Deviation (SD), Standard Error (SE), Confidence Interval (CI), and Coefficient of Variation Percentage (CV), show two more decimals than the collected data. Up to four decimals.
- For percentage data and its mean, median, first quartile (Q1), third quartile (Q3), minimum (min), maximum (max), standard deviation (SD), and standard error (SE), one decimal place is displayed.

P-value display:

- The P-value will be rounded to the nearest number using the decimal places specified below
 - $P \geq 0.0001$, the p value is reported to 4 decimal places.
 - For $p < 0.0001$, report $p < 0.0001$.
 - If $p > 0.9999$, then report > 0.9999 .

The list of all subjects will be sorted by subject number, date and time of visit (if applicable). Data collected on the recording form (e.g., AE) will be listed chronologically among subjects. The treatment group to which the subject was randomly assigned (initial assignment in the IRT system) will be used when listing the intent-to-treat (ITT) population, and the treatment group to which the subject was actually treated (in the EDC) will be used when listing the safety population\pharmacokinetic population. Age, sex at birth, race and ethnicity will be included in the listings.

3.2. Analysis Population

The analysis population defines the subjects included in the analysis. This section contains all analytic populations and their definitions. The subjects included in each population will be determined prior to the unblinding analysis. All tables, figures, and lists will be subtitled with the corresponding analysis population.

For each population, the number and percentage of subjects eligible for inclusion will be summarized by treatment group, as well as the number and percentage of subjects excluded and their primary reason for exclusion.

Subjects who are randomized will be defined as subjects who have filled out the randomization information on the CRF D1 visit randomization page.

3.2.1. Intent-to-treat (ITT) Population

All subjects who are randomized. Subjects are analyzed according to the randomized treatment, regardless of the treatment actually received.

3.2.2. Safety Population (SAF)

All subjects who receive at least 1 dose of study drug during the study. Subjects are analyzed according to the treatment received during the study.

3.2.3. Modified Intent-to-Treat (MITT) Population

The MITT population will serve as the primary population for efficacy analyses in this study. The MITT population is defined as all subjects from the ITT who receive at least 1 dose of study drug.

3.2.4. Microbiologic Modified Intent-to-Treat (micro-MITT) Population

The micro-MITT population is defined as all subjects from the MITT who have a Gram-negative pathogen identified at baseline and the pathogen is susceptible to the investigational medicinal product and comparator.

For cases where multiple gram-negative pathogens (plural organisms) were identified at baseline, all pathogens were only included in micro-MITT if they were susceptible to the test and control drugs.

Only pathogenic bacteria identified in lower respiratory tract samples were considered.

The rules for the processing and derivation of microbiological data, as well as related definitions, are detailed in Section [3.6.2](#).

3.2.5. Carbapenem-resistant Modified Intent-to-Treat (CR-MITT) Population

All subjects from the MITT who have a baseline Gram-negative pathogen identified which is resistant to any carbapenem.

Any one pathogen resistant to any carbapenem antibiotic can be included in the CR-MITT population.

Only pathogenic bacteria identified in lower respiratory tract samples were considered.

The rules for the processing and derivation of microbiological data, as well as related definitions, are detailed in Section [3.6.2](#).

3.2.6. Extended Microbiologic Modified Intent-to-Treat (extended micro-MITT) Population

All subjects from the MITT who have a baseline Gram-negative pathogen identified which is susceptible to either the investigational medicinal product or comparator.

Gram-negative pathogens identified in the extended micro-MITT population need to have at least one susceptible to the test drug or control drug.

Only pathogenic bacteria identified in lower respiratory tract samples were considered.

The rules for the processing and derivation of microbiological data, as well as related definitions, are detailed in Section 3.6.2.

3.2.8. Clinically Evaluable (CE) Population

All subjects from the MITT who receive at least 72 hours of IV study treatment, have an appropriate diagnosis of HABP/VABP, have no important protocol deviations that would affect the assessment of clinical outcome, and have no missing nor indeterminate assessment of clinical outcome.

Based on the above definition, subjects who meet all of the following criteria will be included in the CE population:

- Duration of exposure to study drug ≥ 72 hours .
- Meets Inclusion Criterion 4: Has HABP or VABP, as defined below, requiring intravenous antimicrobial therapy. Note: HABP is defined as symptoms of acute bacterial pneumonia occurring at least 48 hours after hospitalization or within 7 days of discharge from an acute or chronic care facility (e.g., long term care, rehabilitation center, hospital or skilled nursing home). Subjects may have developed acute respiratory failure requiring mechanical ventilation for HABP (vHABP). VABP is defined as acute bacterial pneumonia for which the subject has received mechanical ventilation via endotracheal (or transnasal tracheal) intubation or tracheotomy for ≥ 48 hours.
- Subjects who do not meet Exclusion Criterion 2: Subjects with known or suspected community-acquired bacterial pneumonia, atypical pneumonia, viral pneumonia including novel coronavirus pneumonia (COVID-19), or chemical pneumonia (including

aspiration of gastric contents, inhalation injuries).

- No sustained discontinuation of the test drug \geq for 48 hours (if discontinued and total number of discontinuations < 8).
- No co-prohibition of systemic gram-negative antibiotics for \geq 72 hours (screened based on concomitant medication and co-prohibition regimen deviation data).
- No EOT or TOC Clinical Assessments Uncertain/Missing (Clinical Assessments at EOT and TOC visits may not be Uncertain or Missing. Note: Death resulting in a clinical assessment not being collected is not considered missing).

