8.2. Analysis Populations

There are 9 analysis populations for this study:

Intent-to-Treat (ITT) population: All subjects who are randomized. Subjects are analyzed according to the randomized treatment, regardless of the treatment actually received.

SAF population: All subjects who receive at least 1 dose of study drug during the study. Subjects are analyzed according to the treatment received during the study.

MITT population: The MITT population will serve as the primary population for efficacy analyses in this study. The MITT population is defined as all subjects from the ITT who receive at least 1 dose of study drug.

micro-MITT population: The micro-MITT population is defined as all subjects from the MITT who have a Gram-negative pathogen identified at baseline and the pathogen is susceptible to the investigational medicinal product and comparator.

CR-MITT population: All subjects from the MITT who have a baseline Gram-negative pathogen identified which is resistant to any carbapenem.

Extended micro-MITT population: All subjects from the MITT who have a baseline Gram-negative pathogen identified which is susceptible to either the investigational medicinal product or comparator.

CE population: All subjects from the MITT who receive at least 72 hours of IV study treatment, have an appropriate diagnosis of HABP/VABP, have no important protocol deviations that would affect the assessment of clinical outcome, and have no missing nor indeterminate assessment of clinical outcome.

ME population: All subjects from the micro-MITT who receive at least 72 hours of IV study treatment, have an appropriate diagnosis of HABP/VABP, have no important protocol deviations that would affect the assessment of microbiological outcome, and have no missing nor indeterminate assessment of microbiological outcome.

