3.2.9. Microbiologically Evaluable (ME) Population

All subjects in micro-MITT who received at least 72 hours of intravenous study treatment, had an appropriate diagnosis of HABP/VABP, had no significant protocol deviations that could affect the microbiologic efficacy evaluation, and had no microbiologic efficacy evaluations that were missing or inconclusive.

Based on the above definition, subjects who meet all of the following criteria will be included in the ME population:

- Eligible for micro-MITT population.
- Duration of exposure to the study drug \geq 72 hours.
- Meets Inclusion Criterion 4: Has HABP or VABP, as defined below, requiring intravenous antimicrobial therapy. Note: HABP is defined as symptoms of acute bacterial pneumonia occurring at least 48 hours after hospitalization or within 7 days of discharge from an acute or chronic care facility (e.g., long term care, rehabilitation center, hospital or skilled nursing home). Subjects may have developed acute respiratory failure requiring mechanical ventilation for HABP (vHABP). VABP is defined as acute bacterial pneumonia in subjects receiving mechanical ventilation via endotracheal (or transnasal tracheal) intubation or tracheotomy for ≥ 48 hours.
- Subjects who do not meet Exclusion Criterion 2: Subjects with known or suspected community-acquired bacterial pneumonia, atypical pneumonia, viral pneumonia including novel coronavirus pneumonia (COVID-19), or chemical pneumonia (including aspiration of gastric contents, inhalation injuries).
- No sustained discontinuation of the test drug \geq for 48 hours (if discontinued and total number of discontinuations < 8).
- No co-prohibition of systemic gram-negative antibiotics for \geq 72 hours (screened based on concomitant medication and co-prohibition regimen deviation data).
- No EOT or TOC microbiologic evaluations are indeterminate/missing (Evaluation of microbial efficacy at EOT and TOC visits may not be indeterminate/missing. (Note:

Lower respiratory tract samples are not collected at the EOT/TOC/LFU visit, and microbial efficacy is assessed on the basis of clinical efficacy results and is not missing).

- Only pathogenic bacteria identified in lower respiratory tract samples were considered.

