8.2. Secondary Efficacy Endpoint

The secondary endpoints for this study are the following:

- Day 28 all-cause mortality rate in the MITT population
- Day 14 and Day 28 all-cause mortality rate in the micro-MITT, extended micro-MITT, CE, ME, and CR-MITT populations
- The proportion of subjects with clinical success as evaluated by the investigator at Day 4, EOT, TOC, and LFU visits in the MITT, micro-MITT, extended micro-MITT, CE, ME, and CR-MITT populations
- The proportion of subjects with microbiological success at EOT, TOC, and LFU visits in the micro-MITT, extended micro-MITT, CR-MITT, and ME populations
- The proportional of subjects with microbiological success by pathogen at EOT, TOC, and LFU visits in the micro-MITT, extended micro-MITT, ME, and CR-MITT populations.
- The proportion of subjects with overall success at EOT, TOC, and LFU visits in the micro-MITT, extended micro-MITT, ME, and CR-MITT populations.

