8.2.2. Clinical Outcomes

The assessment of clinical outcome will be assessed by the investigator using the clinical outcome criteria as outlined below and carried out on Day 4, EOT, TOC, and LFU visit.

The clinical response criteria up to TOC visit will be defined as follows:

- **Success:**
 - For Day 4 visit: a subject is alive with resolution or improvement in at least 1 baseline sign/symptom AND no worsening of any baseline signs/symptoms AND no development of new signs/symptoms of pneumonia requiring the initiation of a non-study antibacterial therapy for the index infection.
 - For EOT or TOC visits: a subject is alive with complete resolution or significant improvement of signs and symptoms that were present at baseline and no new signs/symptoms of pneumonia, such that no further antibacterial therapy is necessary.
- **Failure:**
 - For Day 4 visit, persistence or worsening of baseline clinical signs and/or symptoms or the development of new clinical signs and/or symptoms of pneumonia requiring the initiation of a non-study antibiotic therapy or death of the subject.
 - For EOT and TOC visits, persistence, incomplete resolution or no significant improvement of baseline clinical signs and symptoms of pneumonia, and the need for further antibiotic therapy or death of the subject.
- **Indeterminate:** Study data are not available for evaluation of clinical response for any reasons other than due to the lack of clinical improvement or death.

The clinical response criteria at LFU visit will be defined as follows:

- **Sustained success:** Clinical success at TOC and continued resolution or substantial improvement of baseline signs and symptoms of pneumonia, such that no antibacterial therapy has been required for the treatment of pneumonia between TOC and LFU.
- **Failure:** Subject previously assigned a clinical failure or indeterminate at TOC; or relapse defined as clinical success at TOC, but recurrence of signs/symptoms of pneumonia, appearance of new signs and/or symptoms of pneumonia between TOC and LFU, and further antibiotic therapy is warranted or death of the subject.
- **Indeterminate:** Study data are not available for evaluation of clinical response for any reasons other than due to the lack of clinical improvement or death.
The clinical outcomes recorded in the clinical database will be used for analyses.

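### The CE and ME populations require 72 hours of exposure with no exception for death or failure, so deaths before 72 h and failures whose study drug stopped before 72 h drop out of sets in which mortality and Day 4 success are secondary endpoints

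*SAP*

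**What the plan says.** SAP 3.2.8 opens its CE definition with "All subjects from the MITT who receive at least 72 hours of IV study treatment, have an appropriate diagnosis of HABP/VABP". It then turns the definition into a list and states that "subjects who meet all of the following criteria will be included in the CE population". The first item is "Duration of exposure to study drug ≥ 72 hours". SAP 3.2.9 builds the ME set in the same way: "All subjects in micro-MITT who received at least 72 hours of intravenous study treatment". The floor comes from the protocol, whose section 8.2 defines CE as "All subjects from the MITT who receive at least 72 hours of IV study treatment" and sets the same minimum for ME.

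The CE list mentions death once: "Death resulting in a clinical assessment not being collected is not considered missing". That note qualifies the criterion on missing EOT or TOC assessments. It does not touch the separate exposure criterion. The corresponding ME note concerns respiratory samples that were not collected.

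SAP 8.2 lists Day 14 and Day 28 all-cause mortality as secondary endpoints in CE and ME, among other sets. It lists clinical success "at Day 4, EOT, TOC, and LFU visits in the MITT, micro-MITT, extended micro-MITT, CE, ME, and CR-MITT populations". Under SAP 8.2.2, Day 4 failure covers persisting or worsening signs, and new signs "requiring the initiation of a non-study antibiotic therapy or death of the subject". SAP 8.2.2.1 counts death as clinical failure.

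**The concern.** Membership of CE and ME depends on an event after randomization that overlaps with the outcome. A subject who dies before 72 h is a death for the mortality endpoints and a failure for Day 4 success, but is in neither set. The same holds for a subject whose study drug is stopped before 72 h for insufficient effect, which heads the list of discontinuation reasons in protocol 4.3.2.

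Two things are at stake. Mortality is understated and Day 4 success overstated in these sets, relative to the same subjects had they been kept. And if early deaths or failures are more common on one arm, in either direction, the comparison in CE and ME loses part of that difference. The death note in 3.2.8 suggests that deaths were meant to stay in CE; the exposure criterion defeats that for early deaths.

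**Working it through.** **The plan's own figure.** The documents state power only for the primary MITT analysis (SAP 1.3: 450 subjects, 2:1, 10% mortality in both arms, 10% margin, one-sided 0.025, more than 90% power). With an unpooled normal approximation and 300 v 150 subjects, SE = √(0.10×0.90/300 + 0.10×0.90/150) = 0.030. Power = Φ(0.10/0.030 − 1.96) = Φ(1.373) = 91.5%. The figure reproduces and does not depend on CE or ME. The plan states no expected rate for those sets.

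**Where the floor falls.** SAP 3.7.1 makes Day 1 the randomization date, so with a first dose on Day 1, hour 72 falls on Day 4. SAP 6.1 measures exposure as last dose time minus first dose time. On the nominal 6-hourly schedule, 12 doses give 11 × 6 = 66 h and 13 doses give 12 × 6 = 72 h. A subject who dies or is switched on Day 4 before the thirteenth dose is therefore excluded.

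**Mortality, equal arms.** Let p be MITT Day 14 mortality and f the share of those deaths with under 72 h of exposure. Removing only those deaths gives a CE rate of p(1 − f)/(1 − pf). Here p = 10% is from SAP 1.3; f is assumed.

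| f (assumed) | CE mortality | Deaths removed, test (of 30) | Deaths removed, control (of 15) |
|---|---|---|---|
| 10% | 0.09/0.99 = 9.1% | 3 | 1.5 |
| 20% | 0.08/0.98 = 8.2% | 6 | 3 |
| 30% | 0.07/0.97 = 7.2% | 9 | 4.5 |
| 40% | 0.06/0.96 = 6.3% | 12 | 6 |

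**Mortality, unequal arms.** Suppose MITT mortality is 15% v 10%, a 5.0-point difference (assumed).
- f = 20% in both arms: 0.12/0.97 − 0.08/0.98 = 12.4% − 8.2% = 4.2 points.
- f = 40% in both arms: 0.09/0.94 − 0.06/0.96 = 9.6% − 6.3% = 3.3 points.
- f = 40% on test and 10% on control: 9.6% − 9.1% = 0.5 points.

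**Day 4 failure.** Let g be the failure rate in the parent set and s the share of failures with under 72 h of exposure, both assumed. The CE rate is g(1 − s)/(1 − gs).

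| g | s = 25% | s = 50% | s = 75% | s = 100% |
|---|---|---|---|---|
| 15% | 11.7% | 8.1% | 4.2% | 0% |
| 25% | 20.0% | 14.3% | 7.7% | 0% |

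Only s = 100% removes every Day 4 failure, and the plan's definitions do not imply that value.

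**The case against.** The other side has several good points.

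- **Not every Day 4 failure is lost.** A reader might infer that Day 4 failures as such are deleted. The documents do not support this. Persistence of signs can be a failure without study drug being stopped, and membership turns on the interval from first to last dose, not on being on study drug at the Day 4 visit. A failure with at least 72 h of exposure is not removed by this rule.
- **No stated checking role.** A reader might take CE and ME to be the sets that verify the MITT non-inferiority result. Neither document says so. They carry secondary endpoints; the sensitivity analyses in SAP 8.1.2.2 are multiple imputation and survival analysis.
- **An early excess would be visible elsewhere.** SAP 3.2 requires the number excluded from each population, with the primary reason, by arm. The same endpoints are reported in MITT. SAP 8.1.2.2 adds Kaplan-Meier curves in MITT, and SAP 9.1.6.1 tabulates adverse events leading to death.
- **The direction is not fixed.** If early mortality e is equal in both arms and later mortality among the rest is q1 v q2, the MITT difference is (1 − e)(q1 − q2) and the CE difference is q1 − q2, which is slightly larger. Nor is complete disappearance typical. Early deaths of 5% v 2%, with 6% of the rest dying later in both arms, give 10.7% v 7.9% in MITT (2.8 points) and 0 in CE. But that needs 0.05/0.107 = 47% of test-arm deaths before 72 h, above the range used here, and equal later mortality by construction.
- **Early deaths may be few.** Protocol 4.2 excludes life expectancy under 3 days, refractory septic shock and APACHE II above 30. Survivors who stop before 72 h also leave CE, which pushes CE mortality up.
- **Retention has its own selection.** A subject with 6 h of exposure would enter CE after a death or failure, but not after stopping alive for another reason.

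All of this stands and limits the point. None of it supplies the missing exception: a table of exclusions shows an imbalance but does not put the lost events back into the CE and ME rates.

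**Conclusion.** The point holds for deaths before 72 h and for failures whose study drug stopped before 72 h. The floor is a stand-alone criterion in both documents, the death note does not relax it, and the excluded events belong to endpoints analysed in CE and ME. With an assumed 10% to 40% of Day 14 deaths before 72 h, a 10% rate reads as 9.1% to 6.3% in CE. That range counts only the removal of those deaths and takes everyone else in MITT as qualifying for CE. An arm imbalance in early events is reduced or hidden within these sets, though not in the trial as a whole. The consequence is confined to secondary analyses; the primary Day 14 comparison in MITT and the 450-subject calculation do not change. The change is worth making because it is cheap, not because the main conclusion is at risk.

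**What to change.** - In SAP 3.2.8 and 3.2.9, add: *Subjects whose study treatment ended before 72 h because of death or investigator-assessed clinical failure are retained and counted as events.*
- State there that the criteria on sustained discontinuation (48 h or more) and on non-study Gram-negative antibiotics (72 h or more) do not remove these subjects for treatment given after the failure. Otherwise those criteria could exclude them again.
- Report the mortality and clinical-success endpoints in CE and ME under both this and the current protocol definition.
- Keep Day 4 success in CE and ME, since the protocol lists it, but label the current-definition result as conditional on reaching 72 h of exposure.
- Give by-arm counts of subjects excluded by the 72 h criterion, split into death, failure and other reasons.
- List the change in SAP section 11, because the current definition is the protocol's own. If the SAP is already final, SAP section 1 requires the change to be documented in the study report.

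The cost is one further derivation of two populations and a second set of tables; no new data are needed. The downside is that short-exposure subjects enter only if they died or failed, so event rates in CE and ME will be somewhat higher. That is why both versions should be shown.
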